## 0 REVISION HISTORY

This statistical analysis plan is amended to reflect the following changes:

- Added imputation rules for missing or partial medication end dates. See [Section 5.4.3](#) for details.
- Added summary of disposition by Sponsor re-classified withdrawal reasons. See [Section 5.5](#) for details.
- Concomitant medications are summarized by indication (motor function, dementia, psychosis, or other). See [Section 5.9.2](#) for details.
- Removed redundant categorical analysis of caregiver burden scale (CBS) data. See [Section 5.11.2](#) for CBS analysis.
- The criteria for markedly abnormal laboratory values was revised to reflect SI unit. See [Appendix B](#) for details.
- Various administrative text revisions to assure clarity.

## 1 INTRODUCTION

This statistical analysis plan covers the detailed procedures for performing statistical analyses and producing tables and listings in the study described in ACADIA Pharmaceuticals Inc. [Protocol ACP-103-015 \(Amendment 6, dated 30 June 2010\)](#).

## 2 STUDY OVERVIEW

### 2.1 General Study Design and Plan

This study will be conducted as a multi-center, open-label extension study. Subjects who have completed blinded treatment in a previous study of pimavanserin in Parkinson's Disease Psychosis (PDP), and who may, in the opinion of the Investigator, benefit from treatment with pimavanserin, will be enrolled in this extension study for safety evaluation. All subjects were required to have a caregiver. Subjects may be enrolled in ACP-103-015 as early as the last visit of the treatment phase of the prior blinded study OR up to 28 days following completion of this blinded treatment period.

Subjects who enroll in ACP-103-015 within one week of completion of the treatment phase of the prior blinded study will not be required to complete a full baseline visit (Day 1) (see [Appendix A](#)).

Subjects who are enrolled greater than one week following completion of the prior blinded study will be required to complete a full baseline evaluation for ACP-103-015.

Once per day, subjects will be administered 40 mg of pimavanserin (two 20 mg tablets), orally, preferably in the morning. Dose changes (increases or decreases) will NOT be allowed.

All subjects will be required to visit the study site at Week 2, Month 1, Month 3, Month 6, Month 9, Month 12, and every six months thereafter (every 3 months before Protocol

Amendment 6) to complete safety and clinical evaluations. Unscheduled clinical evaluations may occur at any time if deemed appropriate by the Investigator.

## 2.2 Study Procedures (Based on Protocol Amendment 6)

Before any subjects may be enrolled in the study, ACADIA and/or designee must obtain a copy of essential documents including the following:

- Institutional Review Board (IRB) or Ethics Committee (EC) approval of the protocol;
- IRB- or EC-approved Informed Consent Form (ICF);
- Health Insurance Portability and Accountability Act (HIPAA) form (where appropriate);
- Other documents required by local regulations, as applicable.

Each subject must sign the approved ICF and, where appropriate, HIPAA forms prior to the administration of any measures required for this clinical study. Each subject's caregiver signed and dated an ICF. Each subject who meets all eligibility criteria will be assigned a unique identification number. No subject will be enrolled more than once in the study. Once the identification number has been assigned to a subject, no attempt should be made to use that number again.

The baseline day (Day 1) will represent the first day of the study and the first day of dosing with study drug in the ACP-103-015 study. Baseline evaluations will be conducted on Day 1, prior to administration of the first dose of study drug on that day. All subjects will be dosed with 40 mg of pimavanserin administered orally, once per day.

All subjects will be required to visit the study site at Week 2 (Day 14  $\pm$  3 days), Month 1 (Day 28  $\pm$  3 days), Month 3 (Day 84  $\pm$  7 days), Month 6 (Day 168  $\pm$  7 days), Month 9 (Day 252  $\pm$  7 days), Month 12 (Day 336  $\pm$  7 days), and every six months (every 168 days  $\pm$  7 days) thereafter to complete safety and clinical evaluations. (Note: Prior to Amendment No. 6, 30 June 2010, subjects had study visits beyond Month 12 performed every 3 months). Unscheduled clinical evaluations may occur at any time if deemed appropriate by the Investigator. If the subject terminates the study at any time other than a planned visit the subject will be required to visit the clinic for an end-of-study evaluation.

Blood samples for determination of pimavanserin plasma concentration will be obtained prior to study drug administration at Week 2, Month 1, Month 2, Month 3, Month 6, Month 9, Month 12, and every 6 months thereafter, and at end-of-study, .

Safety assessments (clinical safety laboratory tests, vital sign measurements, physical examinations, and electrocardiograms [ECGs]) will be conducted at scheduled times throughout the study. Adverse events (AEs) and the use of concomitant medications will be monitored from the time of informed consent through the final visit.

[Appendix A](#) displays the schedule of events and assessments.

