3. STUDY DESIGN

3.1 Overall Study Design

Pimavanserin will be administered once daily at a fixed dose level of 40 mg. The study will be conducted on an outpatient basis.

Subjects who have completed the treatment period of a previous blinded study of pimavanserin in PDP subjects and who may, in the opinion of the Investigator, benefit from continued treatment with pimavanserin will be enrolled in this study for safety evaluation. Subjects may be enrolled in this study as early as the last visit of the treatment phase of the previous study OR up to 28 days following completion of the treatment period.

Subjects will be required to visit the clinic on Week 2 (Day 14 ± 3 days), Month 1 (Day 28 ± 3 days), Month 3 (Day 84 ± 7 days), Month 6 (168 days ± 7 days), Month 9 (252 days ± 7 days), Month 12 (336 days ± 7 days) and every six months thereafter (every 168 days ± 7 days). Unscheduled clinical evaluations may occur at anytime if deemed appropriate by the Investigator. If the subject terminates the study at any time other than a planned visit the subject will be required to visit the clinic for an end-of-study evaluation.

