### **5.4 Analysis Visit Window, Time Periods and Missing Values**

#### **5.4.1 Visit Windows for Clinical Rating Scales**

For clinical rating scales (e.g. SAPS associated scores, CGI associated scores and CBS) measured between first dose date and last dose date + 3, data will be summarized using the derived visit based on the visit windows shown in [Table 1](#).

Nominal visits as specified in [Appendix A](#) will be re-assigned to the derived visits. The re-assigned visit will be referred to as the ‘derived visit’ as identified in Table 1 below. After reassignment of a visit, if there are multiple assessments for the same visit, the assessment nearest to the target study day will be kept for analysis. In the event of a tie, the assessment from the earlier study day will be kept for analysis. Unscheduled visits are included in the visit re-assignment.

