#### 5.4.2 Summary Time Periods for Safety Results

For safety assessments (AEs, laboratory tests, vital signs, ECG data, UPDRS II+III and physical examinations), the data summary will be based on chronological time periods as defined in [Table 2](#). Rules for determining the analysis values within each time period are detailed in [Section 5.13](#).

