## **5.5 Subject Enrollment and Disposition**

Subject enrollment by protocol amendments and subject counts by study center and prior study will be summarized.

A summary of subject disposition will display the number of subjects enrolled, received study drug, and remained in the study (using visit dates recorded on the vital signs CRF) at the beginning of the following time periods: first 4 weeks (Study Days 1 to 28), 1 to 3 months (Study Days 29 to 91), >3 to 6 months (Study Days 92 to 183), >6 month to 1 year (Study Days 184 to 365), >1 to 2 years (Study Days 366 to 730), >2 to 3 years (Study Days 731 to 1095), >3 to 4 years (Study Days 1096 to 1461) and >4 years (Study Days >=1462). Also included in this summary will be subject discontinuations showing the number of subjects who terminated from the study according to the reason for study termination/discontinuation (Investigator reported and Sponsor re-classified). Reasons for study termination will also be summarized by the time period specified above.

The withdrawal reasons as reported by the investigators on the eCRF are:

- Adverse event
- Death
- Disease progression
- Subject's voluntary withdrawal of consent (Voluntary withdrawal of consent)
- The Investigator determines that continuation in the study would be detrimental to a subject's well-being because of development of a serious illness, any other significant change in clinical status, or any other compelling medical reason (Investigator decision)
- Subject fails to comply with protocol requirements (Subject non-compliance)
- Lost to follow-up
- At discretion of Sponsor (Sponsor decision)

To better understand the discontinuation pattern, ACADIA reviewed the withdrawal reasons and in some cases, on the basis of verbatim comments in the eCRF, re-classified the reasons for discontinuation using the following categories:

- Adverse event
- Death
- Lack of efficacy / PDP progression
- PD /Concomitant disease progression
- Voluntary withdrawal of consent
- PDP improvement
- Investigator decision
- Subject non-compliance
- Lost to follow-up
- Sponsor decision

Subject disposition and study completion by Investigator-specified and Sponsor-reclassified reasons for termination will be presented in data listings and summary tables. Dispositions will also be summarized by 3 regions: North America (US and Canada), Europe and India.

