### **5.13.3 Clinical Laboratory Data**

Observed clinical laboratory data and change from baseline values will be summarized by time period for hematology, chemistry and numeric urinalysis using the periods specified in Section 5.4.2 Table 2. For each laboratory parameter collected for each subject, within each time period, 2 different representations will be used for generating

the population summary statistics: the highest and lowest measurement from that subject during that particular time period. The highest or lowest measurement will capture the worst or the most extreme observed value (depending on the laboratory test, the highest or lowest or both can be concerning). In addition to each time period, for each laboratory parameter, the last, highest and lowest measurement collected for each subject during the entire study period will also be summarized.

For a subset of clinical laboratory parameters (red blood cell count, hemoglobin, white blood cell count, neutrophils, alkaline phosphatase, alanine aminotransferase, aspartate aminotransferase, bilirubin (total), gamma-glutamyl transferase, creatine phosphokinase, lactate dehydrogenase, blood urea nitrogen, creatinine, and uric acid) low [L], normal [N] or high [H] status will be determined based on the normal ranges provided by the testing laboratory.

The count and percentage of subjects with markedly abnormal post-baseline clinical laboratory parameters tabulated for all subjects and a subset of subjects with normal baseline will also be presented by time period and overall as defined in [Table 2](#) and for overall study period. The criteria for markedly abnormal laboratory values are provided in [Appendix B](#). For each laboratory parameter, within each specified time period and for overall study period, if a subject has at least 1 measurement meeting the marked abnormal criterion, this subject will be counted as having an incidence. The denominator for each laboratory parameter within each specified time period will be the total number of subjects with baseline and at least 1 post-baseline value within that particular time period.

Clinical laboratory data will be displayed in data listings with date and study day of collection. All units will be displayed according to the Système International (SI) conventions for units. Out-of-range values will be flagged in the data listings (i.e., 'L' or 'H').

The routine laboratory panel includes:

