#### **5.13.4.2 Orthostatic Hypotension**

Orthostatic hypotension is assessed each time vital signs are collected for pulse and blood pressure through the comparison of 5 minute supine results against 1 minute standing. The count and percentage of subjects experienced orthostatic hypotension as defined below will be summarized for each time period defined in [Section 5.4.2 Table 2](#) and for overall study period (at any timepoint postdose) for subjects for whom orthostatic hypotension was not present at baseline. If a subject has at least 1 measurement meeting the orthostatic hypotension criteria during a given time period, this subject will be counted as having an incidence for that time period. The denominator for percentages is the number of subjects with non-missing data at each visit.

Orthostatic hypotension occurs if:

- there is a decrease of  $\geq 20$  mmHg in systolic blood pressure (SBP)  
OR
- there is a decrease of  $\geq 15$  mmHg in diastolic blood pressure (DBP)  
OR
- there is an increase of  $\geq 20$  bpm in pulse rate (PR);

each measured from 5 minutes supine to 1 minute standing at the same visit.

An overall count and percentage of subjects experienced orthostatic hypotension based on findings from either AE records (i.e. where the preferred term = 'Orthostatic

hypotension') or vital signs (orthostatic changes in blood pressure and pulse) will also be presented. Data listing of blood pressure and pulse measurements for these subjects will also be presented.

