**Table 3. ECG Parameter Normal Ranges**

ECG Parameter (unit)	Normal Range
QRS Interval (msec)	60 – 100
QTcF (msec)	<500
QTcB (msec)	<500
QT Interval (msec)	360 – 470
PR Interval (msec)	120 – 200
R-R Interval (msec)	550-1500
Heart Rate (beats per min)	40 – 110

The proportion of subjects with QTcF  $\leq$  450 msec, 451 -  $\leq$  480 msec, 481 -  $\leq$  500 msec and  $>$  500 msec, and QTcF change from Baseline  $<$ 10 msec, 10 - 29, 30 - 59 msec, and  $\geq$  60 msec will be summarized by time period and overall (at any timepoint postdose). For each ECG parameter, within each specified time period, if a subject has multiple results, the worst (longest interval) measurement within the time period will be used as the analysis value.

All summaries will also be performed in subgroups by gender.

Listings of the ECG parameters, including QTcB, as described above will include date and time of collection, observed values, and flag indicators for any value outside of the normal range (L for below normal, H for above normal).

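### Pooling two visit schedules under any-value and worst-value rules can raise the >1–2 year lab, orthostatic and ECG columns and produce an apparent fall after year 2

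*SAP*

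**What the plan says.** Protocol 3.1 sets visits after Month 12 at "every six months thereafter (every 168 days ± 7 days". SAP 2.2 adds that "Prior to Amendment No. 6, 30 June 2010, subjects had study visits beyond Month 12 performed every 3 months". SAP 2.1 describes the visits, on either schedule, as being for safety and clinical evaluations.

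For safety data, SAP 5.4.2 says "the data summary will be based on chronological time periods as defined in" its Table 2. The late periods are the ones also used for disposition in SAP 5.5: ">1 to 2 years (Study Days 366 to 730), >2 to 3 years (Study Days 731 to 1095", and so on. Within a period the rules are:

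- Laboratory (SAP 5.13.3): "if a subject has at least 1 measurement meeting the marked abnormal criterion, this subject will be counted as having an incidence". The denominator needs only a baseline and one value in the period.
- Orthostatic hypotension (SAP 5.13.4.2): "If a subject has at least 1 measurement meeting the orthostatic hypotension criteria during a given time period, this subject will be counted".
- QTcF categories (SAP 5.13.5.1, after Table 3): "the worst (longest interval) measurement within the time period will be used as the analysis value".
- ECG interpretation (SAP 5.13.5.2): one clinically significant record is enough.
- Continuous laboratory, vital-sign and ECG summaries: each subject's highest and lowest value in the period. The last value is summarized only over the whole study.

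The rating scales are handled differently. SAP 5.4.1 and Table 1 put them on a fixed visit grid, and where several assessments fall in one window, "the assessment nearest to the target study day will be kept for analysis". The laboratory, vital-sign and ECG data have no such table. SAP 6 lists only the SAS version as a departure from the protocol.

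**The concern.** The chance that a subject has at least one abnormal value, and the expected size of a subject's maximum, both grow with the number of measurements. If one column contains subjects measured four times and the next contains subjects measured twice, the two differ even when the risk per visit is constant.

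Long-term safety is the study's only stated objective, and no formal tests are planned, so these descriptive columns are where a reader looks for trends over time. An artefact that lifts year 2 makes later years look better, which is the reassuring direction.

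**Working it through.** The plan states no rate or sample size to reproduce (SAP 2.4 is marked not applicable), so the check starts from the schedule.

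**1. Scheduled visits per period.** Old schedule: day 336 + 84k, taking 3 months as 84 days as Protocol 3.6.2.4 does. New schedule: day 336 + 168k.

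| Period (days) | 3-monthly | 6-monthly |
|---|---|---|
| >6–12 months (184–365) | 2 (252, 336) | 2 (252, 336) |
| >1–2 years (366–730) | 4 (420, 504, 588, 672) | 2 (504, 672) |
| >2–3 years (731–1095) | 5 (756, 840, 924, 1008, 1092) | 2 (840, 1008) |
| >3–4 years (1096–1461) | 4 (1176, 1260, 1344, 1428) | 2 (1176, 1344) |

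Day 1092 can leave its period within its ±7-day window.

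**2. Which column mixes the schedules.** Protocol 1.2 gives 77 subjects past 12 months and 6 past 24 months on 1 May 2010, two months before the amendment. The mixing therefore falls mainly in >1–2 years.

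**3. Subject-level rate.** Assume a 5% chance of an abnormal value per visit (not in the documents). For independent visits the rate over m visits is 1 − 0.95^m. For correlated visits a beta-binomial is used with intraclass correlation ρ. The column rate is (1 − s) × rate(2) + s × rate(4), with an assumed share s of 10–40% fully on the old schedule.

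| Correlation | 2 visits | 4 visits | Column, s = 10% | Column, s = 40% |
|---|---|---|---|---|
| 0 | 9.8% | 18.5% | 10.6% | 13.3% |
| 0.5 | 7.4% | 10.1% | 7.6% | 8.4% |
| 0.8 | 6.0% | 6.8% | 6.0% | 6.3% |
| 1.0 | 5.0% | 5.0% | 5.0% | 5.0% |

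Example (unrounded inputs): 0.6 × 9.75 + 0.4 × 18.55 = 13.3.

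**4. Partial exposure.** Many of the 77 were only partway through year 2. Suppose a subject's switch falls uniformly over days 366–730 (assumption; site switch dates are not given).

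- The day-420 visit occurs with probability 310/365 = 0.849 and the day-588 visit with 142/365 = 0.389.
- Mean visits are 2 + 0.849 + 0.389 = 3.24. The shares with 2, 3 and 4 visits are 15%, 46% and 39%.
- Independent visits: three visits give 1 − 0.95³ = 14.3%, so the average is 0.151 × 9.75 + 0.460 × 14.26 + 0.389 × 18.55 = 15.3%. The column reads 10.3–12.0% against 9.8%.
- Correlation 0.5: three visits give 8.9% and the average is 9.1%. The column reads 7.6–8.1% against 7.4%.

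**5. Is 10–40% plausible?** If 150–400 subjects reach year 2 (assumption), 77 is 51–19% of them. Scaling by the fraction of extra visits made, 1.24/2 = 0.62, gives roughly 32–12% in full-schedule equivalents. Subjects passing Month 12 between 1 May 2010 and their site's switch would add to this.

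**6. QTcF.** The expected maximum of n independent normal values is 0.56 SD above the subject's mean for n = 2 and 1.03 SD for n = 4, a gap of 0.47 SD. With an assumed within-subject SD of 10–15 msec, that is 5–7 msec between a fully old-schedule and a fully new-schedule subject. In the column mean it is 0.10 × 4.7 = 0.5 msec to 0.40 × 7.0 = 2.8 msec.

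**The case against.** Four points against the concern have weight.

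- **Extremes are deliberate.** SAP 5.13.3, 5.13.4.1 and 5.13.5.1 say they are meant to capture the worst value, which is a sound convention for detecting abnormality. This stands, and the tables should stay. It does not make columns with unequal sampling comparable.
- **The effect may be small.** Abnormal laboratory and ECG values tend to persist within a subject, and at full persistence the effect is zero. This also stands, and no formal test or error rate is affected.
- **The superseded visit schedule is not in the file.** SAP 2.1 describes the 3-monthly visits as safety and clinical evaluations, and SAP 5.13.4.1 has vital signs at every visit. That laboratory tests and ECGs were done at every old-schedule visit is a reasonable inference, not a documented fact.
- **Disclosure might suffice.** A footnote, or the number of assessments per subject per period, would warn the reader. It would not supply a readable trend.

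A reader might infer from the counts of 5 and 4 that the >2–3 and >3–4 year columns are inflated too. With 6 subjects past 24 months on 1 May 2010, those counts are nearly hypothetical. A reader might also infer that a real late rise would be hidden throughout. The >6–12 month column has 2 scheduled visits under either schedule, as each later year has under Amendment 6, so it remains an unaffected reference.

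**Conclusion.** The mechanism is supported: the interval doubled, the period tables use any-value or extreme-value rules, and nothing adjusts for the number of assessments. The reach is mainly one column, >1–2 years, which can sit too high against both neighbours and so suggest a fall afterwards.

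The size is not determinable from the documents because the per-visit rate, the correlation and the old-schedule share are all assumed. At 5% per visit and a 10–40% share, the excess runs from about 0.9–3.5 percentage points with independent visits, through 0.3–1.1 points at correlation 0.5, to 0.4 points or less at 0.8. Partial exposure reduces each. The 5–7 msec QTcF gap is between two individual subjects and should not be read as a column effect; the column shift is about 0.5–2.8 msec. This is a worthwhile, inexpensive improvement to a descriptive analysis, not a flaw that invalidates it.

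**What to change.** In SAP 5.13.3, 5.13.4 and 5.13.5.1, keep the highest/lowest and any-value tables. Add one descriptive table per domain (laboratory, vital signs with orthostatic change, ECG) on the SAP Table 1 derived-visit grid. Use one value per subject per visit, nearest the target day, and show observed value, change from baseline and percent meeting the criterion. State that time trends are read from these tables.

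The grid removes the dependence on schedule. Day 420 falls in the Week 48 window (295–421), where day 336 is nearer the target of 337. Day 588 falls in the Week 72 window (422–589), where day 504 is nearer 505. Each subject contributes at most one value per grid visit under either schedule.

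The cost is SAP wording and a few extra tables on windows the SAP already defines. The downside is that off-grid values appear only in the extreme-value tables and listings.

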### **2.3 Randomization and Blinding**

Not applicable.

### **2.4 Sample Size Estimation**

Not applicable.

